Study Design:	
Multi-center, randomized, sham, double-blind.
 
This trial will randomize 112 subjects into 4 equal groups: bilateral continuous wave (BCW), bilateral pulsed wave (BPW 1-2) and SHAM. All subjects, investigators (except the study statistician) and outcome assessors will be blinded to group assignments. The device operator will be aware of group assignments.
 
All subjects will receive 3 NIR-TLT sessions per week for 6 weeks. A follow-up evaluation will be performed 2 weeks after the end of the study. The treatment will follow these specifications: wavelength 830 nm; average irradiance 54.8 mW / cm²; average fluence of 65.8 J / cm² (according to the parameters used in the ELATED-2 study at MGH with the Omnilux New U device), being the total fluence delivered: 3.6 kJ (bilateral) or 1.8 kJ (unilateral), either on the subject's forehead, at or near the electroencephalography (EEG) sites F3 and F4.
 
All NIR-TLT sessions will be 429 seconds (7.15 minutes), regardless of group assignment.

Study population:	
Patients eligible to participate in the study will be diagnosed with MDD by DSM criteria (MINI). Subjects will be between 18 and 75 years of age (not yet 76 years of age) on the date of the examination.

Duration of participation:	
Research subjects will remain in the study for 8 weeks. (6-week treatment period, plus 2-week follow-up). The total duration of the study will be 24 months.

Near Infrared Transcranial Laser Therapy in Subjects with Major Depressive Disorder: A study of Dosing with Laser.

Criteria for valuation:

- **Main:** Improvement of depressive symptoms from each of the four doses of NIR-TLT. Assessed using HAMD-17, at 3 time points (visit 1, visit 9 and visit 18).
- **Secondary:** Safety and tolerability. Assessed by SAFTEE- SI (self-assessed), and collection of serious adverse events throughout the study. Safety data will be used to assess the tolerability of each of the NIR-TLT doses.
Changes in brain electrophysiology (electrical activity): Commercially available EEG devices will be used to collect data on brain electrical activity. At 3 time points (visit 1, visit 9 and visit 18).
- Changes in measurements of MDD symptom severity assessment scales:
 - Doctor Administered Scales: QIDS-C and CGI-S
 - Patient-reported scales: ASQ and SDQ

Entry Criteria:

Inclusion Criteria

1. The age of the subjects in the examination will be between 18 and 75 years (inclusive).

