4.1 Study Aims

Primary Aim:

A. To evaluate and compare the effect(s) of each of the four doses of NIR-TLT on depressive symptomatology: antidepressant effect, in patients with major depressive disorder (MDD).

Hypothesis 1: Total HAM-D 17 scale scores will vary in a NIR-TLT dose-dependent manner, with BPW dose being more effective.

We also expect to be able to estimate the effect size of the antidepressant action as a function of the irradiance applied to the NIR-TLT skin, with the BPW dose being more effective.

Secondary Aims:

B. Compare safety and tolerability at each dose of NIR-TLT.

Hypothesis 2: The doses of NIR-TLT tested in this study will be safe and well tolerated by patients with MDD, as assessed by SAFTEE-SI and reports of serious adverse events. We do not anticipate dose-dependent differences in reported side effects.

C. To compare the effect(s) of each of the four doses of NIR-TLT on brain electrophysiology.

Exploratory Aim:

D. To describe the findings visualized in PET, related to the brain metabolism of the participants, before and at the end of the intervention under study.

4.2 Rationale for the use of the EXPi device:

Transcranial photobiomodulation (t-PBM) with near infrared (NIR) laser therapy has emerged as a possible antidepressant treatment in both animal models (Mohammed et al.2016; Salehpour 2016-2017; Xu et al.2017; Wu et al.2012), and in human studies (Cassano 2015- 2017; Caldieraro et al.2018) t-PBM. NIR appears to increase brain metabolism (by activating the cytochrome C oxidase in the mitochondria), to increase neuroplasticity and to modulate the

Near Infrared Transcranial Laser Therapy in Subjects with Major Depressive Disorder: A study of Dosing with Laser.

endogenous opioids, while decreasing inflammation and oxidative stress. (Chung et. al. 2012; Yu et. al. 1997; Oron et al. 2007, Mochizuki et al. 2002) t-PBM penetrates deep into the cerebral cortex, modulates cortical excitability, and improves cerebral perfusion and oxygenation. The safety of t-PBM has been studied in a sample of 1410 acute stroke patients, with no significant difference in adverse event rates between t-PBM and sham exposure. (Hacke et al. 2014; Lamp et al. 2007, Zivin et al. 2009) Uncontrolled studies suggest an antidepressant effect of t-PBM in subjects suffering from MDD (Cassano 2015-2017; Caldieraro et al. 2018).

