4.9.2 Treatment Visits 1 to 18 -Visits 1-6

Regular treatment visits (1 to 18) occur on non-consecutive days, 3 times per week for 6 weeks.

Purpose: The purpose of the treatment visits is to administer NIR-TLT and collect data to assess the effect of each of the NIR-TLT dose effects on MDD symptomatology (antidepressant effect) and tolerability.

Procedures: Trained study personnel will deliver NIR-TLT to study participants. Treatment visits are estimated to last approximately 429 seconds (7.15 minutes) and will take place in a dedicated NIR-TLT (laser safety) office. Only the subject and the staff administering NIR-TLT will be present during the session. The subject will lie comfortably on an examination bed or sit in a recliner, a cervical pillow (U-shaped) may be used for comfort and to prevent the helmet connector cables from being stepped on, bent or damaged. The NIR-TLT application sites (left and right forehead) will be inspected for skin lesions (e.g., lacerations or signs of inflammation) that might contraindicate treatment. During treatment sessions, a warning sign will be hung on the office door. Ideally the place where treatment is administered should be at a temperature of 25°C +/- 2°C.

Prior to treatment with the EXPi device, the subject's forehead is cleaned with 70% isopropyl alcohol, the cap is placed on the subject's head and secured, and the treatment beam locations are adjusted to match the F3 and F4 EEG sites (or very close if the site is covered by hair), the eyebrows may be used as a reference for placement of the lower edge of the helmet. The operator and subject are provided with appropriate laser safety glasses (optical density rating > 5.0 at 808 nm). Disposable caps may be used for hair control if necessary.

Trained personnel administering NIR-TLT will make every effort to never shine light into or near the subject's eyes. Patients and staff will wear safety glasses selected for the biophysical properties of NIR-TLT in accordance with Occupational Safety and Health Administration (OSHA) guidelines. The patient may sleep during the time of therapy administration.

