The NIR-TLT delivery is expected to last no longer than 7.15 minutes (429 seconds) in total (simultaneous application to the left and right forehead). The subject will be allowed to rest for 5 minutes after NIR-TLT delivery. The skin at the application sites will be inspected again after laser application. A log will be kept with the dates of delivery of the NIR-TLT.

Near Infrared Transcranial Laser Therapy in Subjects with Major Depressive Disorder: A study of Dosing with Laser.

treatment per study subject. The use of cell phones, tablets, computers or electronic devices will not be allowed during laser administration.

[figure not shown]
During treatment visits and prior to NIR-TLT, study personnel will collect tolerability (safety) and efficacy data:

1. Safety data: SAFTEE-SI (self-assessed), C-SSRS, adverse events and concomitant medication form.
2. Efficacy data - HAMD-17.

In addition to the evaluation described above, during visits 1, 9 and 18:

Prior to the NIR-TLT study, the staff will collect primary efficacy data from metric measurements and brain electrophysiology data:

1. Efficiency data:
 - a. Doctor-administered scales (1): HAMD-17, QIDS-C and CGI-S.
 - b. Patient-Reported Scales (1): ASQ and SDQ
2. Brain Electrophysiology Data - Study personnel will conduct a first 10-minute EEG recording session, treat the patient according to their NIR-TLT group randomization, and then conduct a second 10-minute EEG recording session as soon as possible after the end of treatment, but within 15 minutes.

3. Exploratory PET scan data: A PET scan will be performed on the participants selected to be part of the research subgroup, before the first treatment visit and within 24 hours of the end of the last intervention (visit 18).

4.9.3 Follow-up visit (Post Treatments) - Week 8

Near Infrared Transcranial Laser Therapy in Subjects with Major Depressive Disorder: A study of Dosing with Laser.

The next visit will occur two weeks after the last cerebral blood flow impact visit.

Purpose: The purpose of the follow-up visit is to evaluate the long-term antidepressant effect of NIR-TLT.

Procedures: During the follow-up study, staff will collect tolerability (safety) and efficacy data:

1. Safety data: SAFTEE-SI (self-assessed), adverse events and concomitant medication form.

2. Efficiency data:

- a. Doctor-administered scales (1): HAMD-17, QIDS-C and CGI.
- b. Patient-reported scales (1): SDQ and ASQ.

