4.10 Scales & Forms

We will offer clinical interviews and study forms in Spanish. All scales will explore the last 7 days, except M.I.N.I (lifetime), TSRQ (study duration).

- **(M.I.N.I.)** - The M.I.N.I. is a brief structured diagnostic interview, developed jointly by psychiatrists and clinicians in the United States and Europe, for DSM and ICD psychiatric disorders. With an administration time of approximately 15 minutes, it is designed to meet the need for a short but accurate structured psychiatric interview for clinical trials. According to researchers in the Division of Clinical and Treatment Research at the National Institute of Mental Health (NIMH), the M.I.N.I. is a fully validated and more time-efficient alternative to the Structured Clinical Interview for DSM Disorders (SCID) (Sheehan et al., 1998). Validated in Spanish (Ferrando L. et. al, 1998).
- **Systematic Assessment for the Treatment of Emergent Events (SAFTEE-SI)** - The SAFTEE is a commonly used instrument originally developed by NIMH and adapted into a self-report instrument. The version of the scale we plan to use is the same

Transcranial Near Infrared Laser Therapy in Subjects with Major Depressive Disorder: A Laser Dosing Study.

used by the NIMH-sponsored CO-MED multicenter trial, and systematically examines all potential treatment-emergent side effects and discusses specific adverse symptoms, including suicidal thoughts and behaviors, and self-injurious behavior.

- **Hamilton Depression Rating Scale - 17 items (HAM-D-17)**; Hamilton, 1960

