5.5 Efficacy and Safety Analysis for the Aims

It will be carried out as follows:

A. Antidepressant effect of NIR-TLT doses:

To compare the antidepressant effects of NIR-TLT doses, mean changes in HAM-D 17 scores (for evaluation of the Primary Assessment Criteria) and QIDS-C and CGI-S (for evaluation of the Secondary Assessment Criteria), will be performed for each dose at 3 time points (visit 1, visit 9 and visit 18) will be compared using a repeated measures ANCOVA. A significant ANCOVA interaction in mean score changes between groups will be taken as indicating that the groups have different antidepressant efficacy. If significant ANCOVA interactions are found, paired samples t-tests will be used to explore differences between scores/groups.

Both the full analysis and the analysis by intention will be performed to analyze the severity of depression at the endpoint. Patient attrition and dropout will be analyzed. The possible

Transcranial Near Infrared Laser Therapy in Subjects with Major Depressive Disorder: A Laser Dosing Study.

differences between treatment groups in dropouts will be examined with Fisher's exact test.

B. Brain electrophysiological effect of NIR-TLT doses:

To compare the effects of NIR-TLT doses on brain electrophysiology, changes in EEG spectral power in all spectral bands for each dose at 3 time points (visit 1, visit 9, and visit 18) will be compared using a repeated measures ANCOVA. A significant ANCOVA interaction in mean score changes between groups will be taken as indicating that the groups have different effects. If significant ANCOVA interactions are found, paired samples t-tests will be used to explore differences between groups.

C. Safety and tolerability of NIR-TLT doses:

To compare the safety and tolerability of NIR-TLT doses, mean changes iSAFTEE-SI scores at 3 time points (visit 1, visit 9, and visit 18) will be compared using a repeated measures ANOVA. A significant ANOVA interaction in mean score changes between groups will be taken as indicating that the NIR-TLT doses have different tolerability. If significant ANOVA interactions are found, paired samples t-tests will be used to explore differences between groups.

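### The SAFTEE-SI tolerability comparison in Section 5.5 C uses 2 of 18 post-baseline forms and sees about 36% of treatment days, so it is less able to detect early or transient differences between arms

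*Protocol*

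**What the plan says.** Section 5.5 C sets the systematic tolerability comparison: mean changes in SAFTEE-SI "scores at 3 time points (visit 1, visit 9, and visit 18) will be compared using a repeated measures ANOVA". A significant interaction is read as different tolerability between doses.

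The form is collected far more often than that. Section 4.9.2 lists, for the treatment visits, "Safety data: SAFTEE-SI (self-assessed), C-SSRS, adverse events and concomitant medication form". Section 4.9.3 lists, for follow-up, "Safety data: SAFTEE-SI (self-assessed), adverse events and concomitant medication form". The Table of Assessments agrees and marks SAFTEE-SI in every column from V0 to V19.

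Two further statements fix what each form can see:

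- Timing within the visit (4.9.2): "During treatment visits and prior to NIR-TLT, study personnel will collect tolerability (safety) and efficacy data".
- Recall (4.10): "All scales will explore the last 7 days, except M.I.N.I (lifetime), TSRQ (study duration"). SAFTEE-SI is not among the exceptions.

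The schedule is "Regular treatment visits (1 to 18) occur on non-consecutive days, 3 times per week for 6 weeks" (4.9.2), with follow-up two weeks after treatment ends (4.4; week 8 in the Table of Assessments).

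Section 5.5 C also plans a Fisher's exact test across doses on how often and how severely side effects and adverse events occur. Adverse events are recorded from consent to completion (4.17.1) and presented to the end of the study (5.6).

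**The concern.** Hypothesis 2 in Section 4.1 is to be judged by SAFTEE-SI together with serious adverse event reports, and the protocol adds: "We do not anticipate dose-dependent differences in reported side effects". When the expected result is no difference, a test with low sensitivity can easily be read as support for it.

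The protocol's own background gives reason to look closely. Section 4.3 reports that a 16-session trial found more mild side effects on active treatment, insomnia and irritable mood among them. Section 4.20.1 lists heat and headache, vivid dreams and disturbed sleep. Such effects can appear early or come and go between two widely spaced visits.

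Participants who tolerate treatment badly may also leave early. Someone withdrawn before V9 has no on-treatment score at the three named visits, even though V2-V8 forms and possibly an exit form exist (4.19.1 asks for SAFTEE-SI at the exit visit where possible). Section 5.3 allows for 20% loss overall; the protocol does not say how much of it would fall before V9.

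**Working it through.** The plan gives no coverage figure to reproduce, so the check is a count of forms and days.

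**Inputs.** Analysed visits V1, V9, V18 (5.5 C). Collection at V0 to V19 (4.9.2, 4.9.3, Table of Assessments). Forms completed before the session (4.9.2). Recall of 7 days (4.10). 18 sessions, 3 per week for 6 weeks (4.9.2). V19 at 14 days after V18 (4.4). Weekdays are not given; Monday/Wednesday/Friday is assumed first.

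**Forms.** The V1 form precedes the first session, so V1 is baseline. Post-baseline forms for a completer are V2 to V19, which is 18. The test uses V9 and V18, which is 2.

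**Calendar.** Taking V1 as day 1, sessions fall on days 1, 3, 5; 8, 10, 12; 15, 17, 19; 22, 24, 26; 29, 31, 33; 36, 38, 40. So V9 is day 19, V18 is day 40, and V19 is day 40 + 14 = 54.

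**Windows.** Each form covers the 7 days ending the day before the visit.

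- V1: entirely before exposure, contributing no treatment days.
- V9: days 12-18, containing sessions 6, 7 and 8.
- V18: days 33-39, containing sessions 15, 16 and 17.
- V19: days 47-53, not in the repeated measures test.

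**Coverage by the test.**

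- First session to the day before V18 (days 1-39): 14/39 = 36%. The remaining 25 days (64%) are outside, including all of week 1 (days 1-7) and week 4 (days 22-28).
- First session to the day before follow-up (days 1-53): 14/53 = 26%.
- Sessions falling inside a window: 6 of 18.

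**Coverage by the forms collected.**

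- V2 to V18 together cover days 1-39: 39/39 = 100%.
- Adding V19: (39 + 7)/53 = 46/53 = 87%.
- Days in no window: 40-46, which is 7/53 = 13%. The V18 form precedes session 18, and V19 looks back over only the last 7 of the 14 days that follow.

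**Sensitivity to weekdays.** Tuesday/Thursday/Saturday gives the same fractions. Monday/Thursday/Saturday gives 14/40 = 35%, 14/54 = 26%, and 47/54 = 87% with all forms. The uncovered stretch stays at 7 days, and the sessions inside the analysed windows are the same six.

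**The case against.** The strongest reply is that the SAFTEE-SI test is only one part of the safety assessment. The Fisher's exact test in 5.5 C has no visit limit and names side effects as well as adverse events, so it may draw on SAFTEE-SI reports from any visit. An Adverse Events Form is scheduled at V1 to V19, and patients are told to report problems between visits (4.17.2). V1, V9 and V18 also match the time points of the efficacy and EEG analyses. Effects that persist or accumulate should still show at mid-treatment and at the end.

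Much of this stands, and it limits the point. It does not remove it: the protocol does not say that SAFTEE-SI items feed the Fisher's test. Section 4.10 presents SAFTEE-SI as the instrument that screens systematically for emergent effects, and describes the adverse event form as capturing events related to the laser application. That is narrower than the recording of all events in 4.17.1 and 4.17.3.

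A reader might infer three stronger things, none of which the document supports:

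- *Most of the risk period goes unseen.* This is true of the repeated measures test, not of data collection. SAFTEE-SI covers every treatment day up to session 18; the only collection gap is the 7 days from that session.
- *The test is biased toward confirming Hypothesis 2.* Using fewer time points does not bias the randomised contrast at V9 and V18. What is shown is lower sensitivity to early and transient effects. No power loss has been computed.
- *SAFTEE-SI from other visits is never analysed.* It is outside this test, but the Fisher's test does not exclude it.

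It may also be said that visit-level safety displays belong in the statistical analysis plan, which is not at hand. That would be fair if the protocol were silent, but it names the three time points for this comparison itself.

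**Conclusion.** The point holds in a limited form. The SAFTEE-SI repeated measures test uses 2 of 18 post-baseline forms and sees 14 of 39 to 40 treatment days (35-36%). It omits week 1, the V19 score, and all on-treatment and exit data from participants withdrawn before V9. It is therefore less able to detect early or short-lived differences in tolerability, and a non-significant interaction would be weak support for Hypothesis 2. The other safety analyses lessen this but are not stated to use the instrument.

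A separate and smaller point is that the 7 days from session 18 (about 13% of the time to follow-up) fall in no scheduled SAFTEE-SI window and rest on adverse event reports.

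Assumptions: the weekday pattern (three were tried, with almost the same result); the 7-day recall in 4.10 applies to SAFTEE-SI; V19 is 14 days after session 18; visits are kept as scheduled.

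**What to change.** In Section 5.5 C, compare arms on all post-baseline SAFTEE-SI data (V2 to V19 and exit forms) as change from V1, in a repeated-measures model that keeps participants with incomplete visits. Show the by-visit profile by arm, and keep V9 and V18 as named contrasts.

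Leave the 7-day recall unchanged, and state that the week after session 18 is covered by adverse event reports. Lengthening the recall at V19 would close that gap but would make V19 no longer comparable with V1. A worst-score endpoint is not needed either, since it depends on how many forms each participant completes and so on dropout.

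With the change, SAFTEE-SI coverage in the test rises from 35-36% to 100% of treatment days, and from 26% to 87% of the time to follow-up. The cost is slightly more analysis work. No visit, form or participant burden is added.

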4.9.4 Completion

If, during the study, a subject's CGI-S increases more than 2 points or rises above a score of 5, or if they become actively suicidal according to the C-SSRS scale, the subject will be referred to their treating doctor and advised to start or switch to another FDA-approved antidepressant medication. Such subjects may or may not be terminated from the study, depending on the severity of symptoms, at the clinical judgment of the principal investigator. Subjects who are considered actively suicidal and in imminent danger will be terminated from the study and referred to the appropriate local MGH or NKI emergency room for evaluation and subsequent hospitalization, or, if the subject is appropriate for outpatient monitoring, will be referred to their treating doctor for frequent appointments and follow-up. Each subject will have the investigator's contact information, as well as instructions on how to call emergency services, if necessary. We will encourage subjects to continue enrollment in the study through follow-up visits, regardless of discontinuation of NIR-TLT.

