4.17.2 Safety Monitoring

Study subjects will undergo frequent clinical assessments including depressive scores, concomitant medications, adverse events, and serious adverse events and unexpected device events will be recorded from study entry to completion. In addition, clinicians should monitor the safety of subjects by frequently asking them about their comfort during treatment delivery.

If skin erythema occurs, treatment will be discontinued. Patients will be instructed to contact the principal investigator of the study site or a member of his or her staff at any time between visits regarding adverse events or worsening of symptoms. If at any study visit, the subjects' clinical status significantly worsens from baseline (operationalized as the clinical global impression severity score, CGI-S, of 6 or greater) or if a subject develops active suicidal intent and/or plan, based on the C-SSRS scale and/or the clinical interview, the subject will be referred to the treating doctor to start an antidepressant medication or make appropriate changes in the treatment regimen. If the subject were considered to be in imminent danger as a result of suicidality, he/she would be discontinued from the study and referred to appropriate clinical treatment (see 4.9 Termination).

The two site principal investigators ([name], PI) will have bi-weekly conference calls (which will include all study staff); during these conference calls, they will discuss all adverse event reports to identify any safety concerns, based on such concerns, they may decide to temporarily discontinue study enrollment, modifications to the study protocol or terminate the study.

In addition, a Data and Safety Monitoring Board (DSMB), composed of at least 3 members not directly involved in the study, will review the SAEs annually. The research assistants responsible for data collection and storage will be aware of and comply with all regulatory requirements related to adverse events. In the event that a patient becomes ill or injured as a direct result of study participation, medical care will be provided. All adverse events (and device events) will be tracked to resolution and reported to the MGH or NKI IRB as serious in the event that:

Transcranial Near Infrared Laser Therapy in Subjects with Major Depressive Disorder: A Laser Dosing Study.

1. Not anticipated and possibly study-related (same report as SAE) or

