4.19 Subject Disposition Criteria

4.19.1 Withdrawal from the Study

Each subject and the investigator reserve the right at any time to terminate a subject's participation in the clinical investigation.

Possible reasons for withdrawal or removal from the study may include:

Transcranial Near Infrared Laser Therapy in Subjects with Major Depressive Disorder: A Laser Dosing Study.

1. The subject voluntarily withdraws consent.
2. The subject was ineligible according to the inclusion and exclusion criteria of the study.
3. The subject develops an adverse event that would not allow continuation in the study.
4. The subject has an adverse event that, in the opinion of the investigator, warrants withdrawal from the study. Pthera LLC must be notified within two business days.
5. The subject and/or the investigator make the decision that the subject should withdraw from the study.
6. Subject to death of participant.
7. Positive pregnancy test during eligibility procedures.
8. The subject misses one of the 3 scheduled sessions per week and it is not possible to make it up before the end of the week. When a subject withdraws or is withdrawn from the study, the following will be performed, if possible, at the study termination (exit) visit:
 - HAM-D-17
 - QIDS-C
 - CGI
 - C-SSRS
 - ADVERSE EVENT FORM
 - Concomitant Medication Form
 - ASQ (self-assessment)
 - SAFTEE-SI (self-assessment)
 - SDQ (self-assessment)

For all subjects who prematurely withdraw from the study, the date and reason for withdrawal will be documented.

4.19.2 *Loss of Follow-up*

If a center is unable to contact a subject or if the subject fails to appear for a visit, three documented telephone calls should be made, followed by a certified letter (or its equivalent, such as an e-mail). The certified letter should detail the need for the subject to appear for a visit, the center's failed attempts to contact the subject, and that failure to contact the center will cause the subject to be withdrawn from the study.

If the certified letter is returned to the center as undeliverable or the letter is delivered but the subject does not communicate with the center and no further contact is made with the subject or the subject's caregiver, then the subject will be considered lost to follow-up with the subject and suspended from the study. All attempts to contact the subject will be documented.

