A delay in the application of the laser, not exceeding 72 hours, will be tolerated for reasons of major cause. Provided that this delay allows to comply with the 3 administrations corresponding to the week of the intervention under study. If the subject does not comply with the 3 administrations of the treatment, he/she will be withdrawn from the study.

Transcranial Near Infrared Laser Therapy in Subjects with Major Depressive Disorder: A Laser Dosing Study.

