In addition, the frequency and severity of side effects and adverse events reported for each dose will be compared using a Fisher's exact test. The corrective actions taken by the doctors as well as the clinical judgment on the likelihood of association of the side effect/adverse event with the NIR-TLT dose will also be reported.

D. Findings visualized in the PET scan:

The analysis of the results obtained in the PET will be for exploratory purposes to study the brain metabolism of the participants, before and at the end of the study intervention in the 4 groups. Following the recommendations of Daniel et al. (Daniel, 2012), for the exploratory analysis we will work with a minimum number of 5 participants per group, with a total of 20 participants.

The results obtained in the PET will be presented in a descriptive manner.

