6.4 Monitoring Procedures

Monitoring will be conducted by the PI, who will periodically review laboratory results and clinical information. The PI will coordinate the different phases of protocol implementation, such as application and follow-up. The PI will be in frequent contact with the other staff members responsible for the delivery of the NIR-TLT and with Pthera LLC, who will loan the NIR-TLT device. We have minimized the risks potentially associated with NIR-TLT use by providing subjects and the operator with safety goggles or eye pads during NIR-TLT application and by requiring two methods of contraception (although NIR-TLT has not been associated with a teratogenic effect). We have also included treatment discontinuation rules based on the development of skin erythema or discomfort lasting more than 24 hours at TLT delivery sites (to avoid the risk of the subject having unknown skin photosensitivity)

Treatment will end for participants who experience temporary pain or discomfort during a treatment session that is present up to 24 hours after the end of the session.

Transcranial Near Infrared Laser Therapy in Subjects with Major Depressive Disorder: A Laser Dosing Study.

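### The SAFTEE-SI comparison in 5.5 C uses visits 1, 9 and 18 only, so participants stopped for intolerance and then withdrawn tend to drop out of that one test

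*Protocol*

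**What the plan says.** **The test.** Under 5.5 C, SAFTEE-SI "scores at 3 time points (visit 1, visit 9, and visit 18) will be compared using a repeated measures ANOVA", and a significant interaction is read as a difference in tolerability between doses. The intention-based analysis in 5.5 A is stated for depression severity only.

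**Stopping the laser.** Section 4.17.2, repeated in 6.4.1: "If skin erythema occurs, treatment will be discontinued". Section 6.4: "Treatment will end for participants who experience temporary pain or discomfort during a treatment session that is present up to 24 hours" after the session.

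**Leaving the study.** Section 4.19.1 lists a missed session that cannot be recovered within the same week as a possible reason for withdrawal: "The subject misses one of the 3 scheduled sessions per week and it is not possible to make it up before the end of the" (quote cut short). Section 4.19.2 is firmer: "If the subject does not comply with the 3 administrations of the treatment, he/she will be withdrawn from the study". Neither makes an exception for laser stopped because of intolerance. Section 4.9.4 points the other way: "We will encourage subjects to continue enrollment in the study through follow-up visits, regardless of discontinuation of NIR-TLT".

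**Forms collected.** The Table of Assessments (section 8) has SAFTEE-SI at every visit from selection to follow-up. Section 4.19.1 adds one at the exit visit, if possible. Section 4.10 gives the scales a 7-day recall period, with exceptions that do not include SAFTEE-SI.

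**Other tolerability comparisons.** Section 5.5 C also states that "the frequency and severity of side effects and adverse events reported for each dose will be compared using a Fisher's exact test". Section 5.5 A compares dropouts between groups by Fisher's exact test, and 5.6 tabulates adverse events by group.

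**The concern.** Comparing safety and tolerability across doses is a stated aim. A participant whose laser is stopped for a local reaction, and who is then withdrawn, cannot supply the later forms that the SAFTEE-SI test calls for. The reason for the missing form is then closely tied to what the test is meant to measure.

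Section 4.20.1 lists erythema, pain, discomfort and heat at the application site among events already reported with this therapy, so such stops may be more common in the active arms than under sham. If so, the test compares doses among those who tolerated the laser, and a poorly tolerated dose looks better than it is. The error runs towards what Hypothesis 2 predicts, namely no dose-dependent difference in side effects. A non-significant interaction would then be weak support for that hypothesis.

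**Working it through.** The plan gives no figure for the SAFTEE-SI test that could be reproduced. The 112 participants (4 × 28) in 5.3 are set for HAM-D-17, and only the group size of 28 is used here.

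**Step 1: which forms exist and which are used, if the withdrawal rules are followed**

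| Laser stopped for intolerance | Visit 9 form | Visit 18 form | Other forms collected | In a classical ANOVA on visits 1, 9, 18 |
|---|---|---|---|---|
| Before visit 9 | missing | missing | forms up to the stop; exit form if possible | omitted |
| Between visits 9 and 18 | present | missing | forms up to the stop; exit form if possible | omitted |
| Never | present | present | all visits | included |

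The exit form, which is the one most likely to record the reaction, belongs to none of the three time points.

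**Step 2: if participants stay instead, as 4.9.4 encourages**

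At three sessions a week, visit 9 closes week 3 and visit 18 closes week 6. With a 7-day recall, a visit 9 form does not reach back to a reaction in week 1, and a visit 18 form does not reach back to one in week 4. These later forms would also be off treatment. Staying in the study supplies numbers for the ANOVA but may not record the intolerance.

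**Step 3: possible size**

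The protocol gives neither a stop rate for intolerance nor a SAFTEE-SI standard deviation, so both inputs below are assumptions:
- q = share of an active arm stopped for intolerance, 5% to 20%. The top of the range equals the all-cause loss rate in 5.3, which is not an intolerance rate.
- D = how much worse stoppers score than completers, 1 or 2 SD.

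With completer mean C, the mean of the whole arm is (1 − q)·C + q·(C + D) = C + q·D. The completers-only mean is C, so the arm is understated by q·D.

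| q | Omitted, 28 × q | q·D, D = 1 SD | q·D, D = 2 SD |
|---|---|---|---|
| 5% | 1.4 | 0.05 SD | 0.10 SD |
| 10% | 2.8 | 0.10 SD | 0.20 SD |
| 15% | 4.2 | 0.15 SD | 0.30 SD |
| 20% | 5.6 | 0.20 SD | 0.40 SD |

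For the contrast with sham, if a share s of sham also stops with the same D, the bias is (q − s)·D. It vanishes when the stop rates are equal and equals the tabled value when s = 0.

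**Step 4: what the Fisher test keeps**

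It needs no visit 9 or 18 score, so stopped participants count in full. For one active arm against sham (28 v 28, two-sided 0.05, assumed sham rate 1%), power is about 0.2%, 4%, 19%, 42% and 82% at active event rates of 5%, 10%, 15%, 20% and 30%.

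**The case against.** A reader might infer that people who could not tolerate the laser vanish from the tolerability assessment. The protocol does not support that. Their adverse events enter the Fisher's exact test in 5.5 C, their withdrawal enters the dropout comparison in 5.5 A, and 5.6 tabulates events by group. This objection stands, and it confines the point to the SAFTEE-SI test. The low power in step 4 is a different limitation from exclusion; it only means that the Fisher test is no full substitute at modest event rates.

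A reader might also infer that the whole intolerance signal is lost. That follows only if every stopper is excluded and no one else's score changes, and nothing in the protocol establishes either.

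Further points carry weight:
- Withdrawal is not certain. Section 4.9.4 says the opposite, 4.19.1 lists possible reasons only, and the sentence in 4.19.2 stands among rules on delayed sessions and non-compliance rather than laser stopped by staff.
- Section 4.4 allows shorter irradiation for tolerability, so not every reaction ends treatment.
- The protocol does not say that incomplete cases are deleted. That is how the named method classically works, and an analysis plan that is not shown could handle it otherwise.
- The effect may be small. Section 4.4.2 expects no perceptible difference from sham, 4.3 reports no significant difference in adverse effect rates in 1410 stroke subjects, and a local skin reaction may barely move a broad symptom inventory.

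These points limit certainty and size. They do not remove the fault: the protocol itself names the method and the three time points, and states its intention-based analysis for depression severity only. An analysis plan could repair the test only by bringing in forms from outside those time points.

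**Conclusion.** The point holds for the SAFTEE-SI comparison in 5.5 C and for nothing wider. Followed as written together with the withdrawal rules, that test tends to omit participants stopped for intolerance and is biased towards no difference between doses. This rests on two conditions: a classical, complete-case repeated measures ANOVA, and more such stops in the active arms than under sham, or in one dose than another.

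The documents cannot settle the size. The illustrative range is an active-arm mean understated by about 0.05 to 0.40 SD, with about 1 to 6 of 28 participants omitted; lower stop rates or a smaller D would make it less. Separately, 4.9.4 contradicts 4.19.1 and 4.19.2 on whether a participant remains in the study once the laser is stopped. Until that is reconciled, who contributes to this test depends on which section a site follows. The primary HAM-D-17 sample size and the adverse event comparisons are not touched by this point.

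**What to change.** In 5.5 C, replace the three-visit ANOVA for SAFTEE-SI with a mixed model for repeated measures:
- Include every participant with at least one session and any later SAFTEE-SI form.
- Use all forms collected on treatment and the exit form, each placed at its actual time since visit 1.
- Report the number and share of laser stops for intolerance by arm beside the model result.

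Reconcile 4.9.4 with 4.19.1 and 4.19.2 so that all sites treat these participants alike. Which rule should apply is for the sponsor and investigators, and nothing here changes a clinical stopping rule.

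The cost is wording in the protocol and analysis plan, with no new assessment, because the forms are already in the schedule. The drawback is small: exit forms fall at different times and will be missing for some, since they are collected only if possible. The number of stopped participants without an exit form should therefore be reported too.
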